6.3. Missing Data⁴

For missing FVC data imputation, patients will be classified into different patterns depending on the availability of data:

Patients with a 26 week FVC value:

1. those who received study drug until 26 weeks (completed the treatment period);
2. those who prematurely discontinued study drug, but who were followed up until Week 26.

Patients without a 26 Week FVC value:

3. those who were alive at 26 weeks;
4. those who died before 26 weeks.

Missing data at other visits before Week 26 (primary outcome variable) will not be imputed.

The following imputation methods including sensitivity analyses will be applied for patients with pattern 3 - 4:

Assuming that deaths of the patients (pattern 4) is likely to be related to worsening of IPF, these unobserved FVC values should be lower than those in patients who did not die prior to Week 26.

Methods for handling missing data due to death will include the following:

- Replacement with the worst possible value (FVC= 0 mL or 0%) (Primary analysis).
- Replacement with worst observed averaged FVC value at week 26 (Sensitivity analysis).

⁴ This section is based on the section 6.2 “Summaries of conduct of study” of clinical study Protocol.

ML39355_STATISTICAL ANALYSIS PLAN_Final 2.0_17 June 2020

- Replacement with an intermediate value (FVC =1500 mL or 50%) (Sensitivity analysis).

Missing data due to reasons other than death (e.g., missing visits, early withdrawal from the study, including missing values due to lung transplantations) (pattern 3) will be replaced with imputed values based on the average measurements for “similar” patients at that time point. Similar patients are those without missing data before that time point and whose data have the smallest sum of squared deviations (SSD) from that patient for all visits prior to the one with the missing data. Missing data due to lung transplant will be imputed using the SSD method even if the patient dies after lung transplant.

The procedure referred to as the sum of squared deviations (SSD) is outlined as follows:

Step 1: For post-Baseline missing value to be imputed at a visit (Visit week 26) for a particular patient (Patient A), a set of all patients without any missing values for visits from Baseline up to Visit week 26 as Patient A will be selected.

Step 2: For the patients in this set, the SSDs between each patient selected in Step 1 and Patient A will be calculated across all non-missing values from Baseline up to the visit prior to Visit week 26.

Step 3: The 3 patients with the smallest SSDs will be identified and the average of their non-missing value at Visit week 26 will be used to impute the missing value for Patient A at that visit. The number of smallest SSDs to calculate the average can be less than 3 due to availability of patients defined in Step 1 or more than 3 based on tied SSDs.

A sensitivity analysis will use the data imputed with last observation carried forward method (LOCF).

Complete case analysis will also be performed as a sensitivity analysis.

If the information about end date for prior/concomitant therapy is missing or incomplete, the following rules (table 6.1) will be used for the classification of therapy as prior or concomitant.

Table 6.1 – Management of partial and missing prior/concomitant therapy end date.

Day	Month	Year	Processing
is missing	is known	is known	Therapy will be classified as concomitant, if month and year \geq month and year of the first dose of study therapy, else – as prior
is missing	is missing	is known	Therapy will be classified as concomitant, if year \geq year of the first dose of study therapy, else – as prior
is known	is missing	is known	
is missing	is known	is missing	Therapy will be classified as concomitant
is known	is missing	is missing	
is missing	is missing	is missing	

ML39355_STATISTICAL ANALYSIS PLAN_Final 2.0_17 June 2020

If the information about adverse event start date and time is missing or incomplete, the following rules (table 6.2) will be used for the classification of adverse events as TEAEs and non-TEAEs (occurred before the start of study treatment).

Table 6.2 – Management of partial and missing AE start date.

Day	Month	Year	Processing
is missing	is known	is known	AE will be classified as TEAE, if month and year \geq month and year of the first dose of study therapy
is missing	is missing	is known	AE will be classified as TEAE, if year \geq year of the first dose of study therapy
is known	is missing	is known	
is missing	is known	is missing	AE will be classified as TEAE
is known	is missing	is missing	
is missing	is missing	is missing	

No date imputation will be performed for listings.

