Missing data at other visits before Week 26 (primary outcome variable) will not be imputed.

The following imputation methods including sensitivity analyses will be applied for patients with pattern 3 - 4:

Assuming that deaths of the patients (pattern 4) is likely to be related to worsening of IPF, these unobserved FVC values should be lower than those in patients who did not die prior to Week 26. Methods for handling missing data due to death will include the following:

- Replacement with the worst possible value (FVC= 0 mL or 0%) (Primary analysis).
- Replacement with worst observed FVC value at week 26 (Sensitivity analysis).

Pirfenidone—F. Hoffmann-La Roche Ltd

136/Protocol ML39355, Version 2 dated 09-Jun-2018

- Replacement with an intermediate value (FVC =1500 mL or 50%) (Sensitivity analysis).

Missing data due to reasons other than death (pattern 3) will be replaced with imputed values based on the average measurements for “similar” patients at that time point (Primary analysis). Similar patients are those without missing data before that time point and whose data have the smallest sum of squared deviations (SSD) from that patient for all visits prior to the one with the missing data. Missing data due to lung transplant will be imputed using the SSD method even if the patient dies after lung transplant. A sensitivity analysis will use the data imputed with last observation carried forward method (LOCF).

Complete case analysis will also be performed as a sensitivity analysis.

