6.4.1 Primary Efficacy Endpoint

The primary outcome variable is the absolute change in FVC from Baseline to Week 26 (both in mL and % predicted). Baseline FVC will be the average of the highest FVC measurement recorded at the Screening and Day 1 visits. The FVC at Week 26 will be the average of the highest FVC measurement recorded on two separate days at Week

Pirfenidone—F. Hoffmann-La Roche Ltd

26. Data will be analyzed using a standard descriptive statistics for continuous variables and 95% CI for the mean.

The data imputation methods for primary endpoint are described in [Section 6.2](#).

The distribution (number and percentage) of primary outcome variable by patients across *three* categories of change from Baseline (Decline of $\geq 10\%$ or death before Week 26; *Decline of $< 10\%$ to 0%* ; Improvement of $\geq 0\%$) will be provided in frequency table.

Additionally, the absolute change in FVC from Baseline at Week 12, 39 (optional) and 52 (optional) and mean FVC change through all time endpoints (both in mL and % predicted) will be summarized in tables with standard descriptive statistics for continuous variables and 95% CI for mean.

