4.2. Randomization and Blinding²

Randomization is not planned in the study.

Blinding is not applicable in this open-label study.

5. Sample Size³

Taking into account study design (single group prospective study), sample size was estimated based on feasibility of patient enrollment with precision-based approach. In the ASCEND study primary efficacy endpoint (Percent Predicted FVC) in pirfenidone group changed from 67.8 (11.24) (denoted as mean (SD)) at baseline to 65.3 (14.52) at week 26, with stable disease (decline in FVC < 10 % to 0 %) in 60.1 % of study patients.

The required sample size for two-sided 95% confidence level can be calculated using the following formula:

$$n = \hat{p}\hat{q} \left(\frac{Z_{\alpha/2}}{E} \right)^2 ;$$
$$n = 0.601 \times 0.399 \left(\frac{1.96}{0.125} \right)^2 \approx 58.96.$$

Assuming previous calculations, 60 patients included in the study will be sufficient for study parameters estimation. Taking into account study goals and the notion that the study drug is a product for the treatment of an orphan drug, margin of error of 0.125 is considered sufficient for parameter estimation. For precision-based sample size justification, with a sample size of 60 patients, an expected mean value of 2.5% and standard deviation of 20, distance from the mean to limit of the two-sided 95% confidence interval for the mean Change from Baseline to Week 26 (Percent Predicted FVC) will extend about 5 (margin of error). The SD for change from baseline at week 26 is conservatively estimated based on the results of the ASCEND study as standard deviation for Percent Predicted FVC in pirfenidone group at week 26 (14.52) multiplied by $\sqrt{2}$ (Machin et al., 1997). This is also in line with the results of CAPACITY programme (Noble et al. 2011) in which the SD of changes from baseline was 17 - 20 at week 72.

Taking into account an expected rate of screening failures about 45%, up to 109 patients will be screened for eligibility.

6. General Considerations

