6.6. Multiple Testing

No adjustment for multiplicity is planned.

7. Summary of Study Data

Demographic and other baseline characteristics, efficacy and safety data will be summarized by time point of assessment and listed.

Default Summary Statistics

The default summary statistics for quantitative and ordinal variables will be the number of observations (n), mean, standard deviation (SD), median, minimum (Min) and maximum (Max).

Default Frequency Tabulations

For qualitative variables, the number and percentage (n, %) of patients with non-missing data per category and total number of patients with non-missing data where applicable (n') will be the default summary presentation.

For AEs and medical history, however, the denominator for the percentage calculation will be the number of patients at risk. A patient will be considered at risk if the patient is in the Treated set.

⁵ This section is based on the section 6.6 “Interim analysis” of clinical study Protocol.

ML39355_STATISTICAL ANALYSIS PLAN_Final 2.0_17 June 2020

The number of decimals for each descriptive statistic will be determined by the following rules:

- mean, median: +1 decimal symbols compared to the analysed variable values;
- standard deviation: +2 decimal symbols compared to the analysed variable values;
- minimum and maximum values: the same as for the analysed variable values;
- percentages will be rounded to one decimal symbol;
- confidence intervals will be presented with accuracy of the estimated value.

The maximum number of decimal places in the statistical report is four. If some descriptive statistic has more than four decimal places after above mentioned rules application, this value will be rounded to four decimal places.

Statistical Tests and Common Calculations

Unless otherwise specified in the description of the analyses, the following arrangements will be applied:

- 95% two-sided confidence intervals (CI);
- [if appropriate] CIs for mean values will be calculated based on normal distribution (SAS procedure UNIVARIATE with CIBASIC option);
- [if appropriate] CIs for proportions will be computed using the exact (Clopper-Pearson) method.
- Type I error values (p-values) will be rounded to four decimal symbols.

For descriptive statistics and analysis, the following rules will be applied:

- “<XX” results (e.g. below the limit of quantification, BLQ) will be replaced by the “XX/2” values;

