**ML39355_STATISTICAL ANALYSIS PLAN_Final 2.0_17 June 2020**

two separate days at Week 26, if either is missing, the non-missing value will be used. If both values are missing, the data will be imputed as specified in Section 6.3.

Data will be analyzed using standard descriptive statistics for continuous variables and 95% CI for the means and mean changes.

The data imputation methods for primary endpoint are described in Section 6.3.

For the primary analysis, missing data due to death will be replaced with the worst possible value (FVC= 0 mL or 0%). Missing data due to reasons other than death (pattern 3) will be replaced with imputed values based on the average measurements for “similar” patients at that time point (SSD, Primary analysis).

As sensitivity analyses, the following imputation methods will be used:

1. Missing data due to death will be replaced with the worst observed FVC value at week 26. Missing data due to reasons other than death (pattern 3) will be replaced with imputed values based on the average measurements for “similar” patients at that time point (SSD).

2. Missing data due to death will be replaced with an intermediate value (FVC =1500 mL or 50%). Missing data due to reasons other than death (pattern 3) will be replaced with imputed values based on the average measurements for “similar” patients at that time point (SSD).

3. Missing data due to death will be replaced with the worst possible value (FVC= 0 mL or 0%). Missing data due to reasons other than death (pattern 3) will be replaced with LOCF.

4. Missing data due to death will be replaced with the worst observed FVC value at week 26. Missing data due to reasons other than death (pattern 3) will be replaced with LOCF.

5. Missing data due to death will be replaced with an intermediate value (FVC =1500 mL or 50%). Missing data due to reasons other than death (pattern 3) will be replaced with LOCF.

6. Missing data due to death and due to reasons other than death (pattern 3) will be replaced with LOCF.

Analysis of the primary efficacy endpoint will be also repeated on the Complete case set (CCS) without missing data imputation as the sensitivity analysis. Complete case set will include patients related to pattern 1 and 2 (section 6.3), results will be reported for pattern 1 and 2 separately and overall.

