One (final) statistical analysis report will be prepared in the Microsoft Office Word (.docx) format after the end of data collection and database lock. The results of statistical analysis will be presented in the form of tables, figures and listings in English.

14. Summary of Changes to the Protocol

ML39355_STATISTICAL ANALYSIS PLAN_Final 2.0_17 June 2020

The analyses methods in this SAP are fully consistent with the clinical study Protocol.

ML39355_STATISTICAL ANALYSIS PLAN_Final 2.0_17 June 2020

15. References

- 1) Committee for Proprietary Medicinal Products (CPMP). International Conference on Harmonisation (ICH) Topic E9: Note for Guidance on Statistical Principles for Clinical Trials; September 1998.
- 2) DataMatrix_SOP_STAT001_Statistical Principles_ver.3.0_June 2019.
- 3) DataMatrix_SOP_STAT002_Statistical Analysis Plan Development_ver.2.0_July 2017.
- 4) DataMatrix_SOP_DM010_Dictionary Management and Data Coding_ver.2.0_August 2015.
- 7) ML39355 Study Results Posting Requirements.

ML39355_STATISTICAL ANALYSIS PLAN_Final 2.0_17 June 2020

16. Listing of Tables, Listings and Figures

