SD	XX.XX	XX.XX
Median	XX.X	XX.X
Min	XX	XX
Max	XX	XX

N: the number of patients in the FAS.

n: the number of valid measurements.

Baseline FVC is the average of the pre-bronchodilator FVC measured at the Screening and Day 1 visits. The FVC at Week 26 is the average of the FVC measured on two separate days at Week 26.

*: Values assessed within the corresponding visit window.

Path to the program code, date and time of output

Data extracted: DD.MM.YYYY

<Report the following assessments: Screening (pre-bronchodilator), Day 1, Baseline, Week 12, Week 26 Day 1, Week 26 Day 2, Week 26, Week 39, Week 52>
 <FVC values within the visit window will also be presented descriptively for the following assessments: Week 12*, Week 26 Day 1*, Week 26 Day 2*, Week 26*, Week 39*, Week 52*>
 <Report the following parameters: FVC (absolute), mL/ FVC (relative) predicted, %>

ML39355_STATISTICAL ANALYSIS PLAN_Final 2.0_17 June 2020

 F. Hoffmann-La Roche Ltd
 ML39355

Table 2.2 Primary efficacy endpoint
 Full analysis set (FAS)
 Page X of X

Parameter: XXXXXXXXXXXX, <units>

	Total (N = XX)	Change from the baseline
Baseline		
n	XX	
Mean [95% CI]	XX.X [XX.X - XX.X]	
SD	XX.XX	
Median	XX.X	
Min	XX	
Max	XX	
Week 26, Primary analysis		
n	XX	XX
Mean [95% CI]	XX.X [XX.X - XX.X]	XX.X [XX.X - XX.X]
SD	XX.XX	XX.XX
Median	XX.X	XX.X
Min	XX	XX
Max	XX	XX
Week 26, Sensitivity analysis 1		
n	XX	XX
Mean [95% CI]	XX.X [XX.X - XX.X]	XX.X [XX.X - XX.X]
SD	XX.XX	XX.XX
Median	XX.X	XX.X
Min	XX	XX
Max	XX	XX
Week 26, Sensitivity analysis 2		
n	XX	XX
Mean [95% CI]	XX.X [XX.X - XX.X]	XX.X [XX.X - XX.X]
SD	XX.XX	XX.XX
Median	XX.X	XX.X
Min	XX	XX
Max	XX	XX
...		

N: the number of patients in the FAS.

ML39355_STATISTICAL ANALYSIS PLAN_Final 2.0_17 June 2020

n: the number of valid measurements.

Baseline FVC is the average of the pre-bronchodilator FVC measured at the Screening and Day 1 visits. The FVC at Week 26 is the average of the FVC measured on two separate days at Week 26.

Sensitivity analyses 1 - 6 related to missing Week 26 data imputation are described in SAP Section 8.1; Sensitivity analysis 7 - Primary analysis excluding all FVC values outside of visit window. Sensitivity analysis 8 - Complete case set; Sensitivity analysis 9 - Complete case set excluding all FVC values outside of visit window.

Path to the program code, date and time of output

Data extracted: DD.MM.YYYY

<Report the following parameters: FVC (absolute), mL/ FVC (relative) predicted, %>

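### The primary 95% CI counts single SSD-imputed Week 26 FVC values as observed and is too narrow: with no deaths, coverage is about 93% at 10% missing and 90–92% at 20%

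*SAP*

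**What the plan says.** Protocol 6.2 sets the primary handling for patients alive at Week 26 without an FVC (pattern 3): "Missing data due to reasons other than death (pattern 3) will be replaced with imputed values based on the average measurements for" similar patients. SAP 6.3 turns this into a three-step algorithm. Donors have complete FVC from Baseline to Week 26 and are ranked by squared distance on the earlier visits. The final step reads: "The 3 patients with the smallest SSDs will be identified and the average of their non-missing value at Visit week 26 will be used". Fewer donors are allowed if few are available, and more if distances tie. SAP 8.1 confirms this as the primary imputation. Deaths are scored as 0 mL or 0%.

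Protocol 6.4.1 describes the analysis of the completed data: "Data will be analyzed using a standard descriptive statistics for continuous variables and 95% CI for the mean". SAP 7 supplies the formula: "CIs for mean values will be calculated based on normal distribution (SAS procedure UNIVARIATE with CIBASIC option").

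SAP 8.1 lists six alternative imputation rules, all single-value. It adds: "Analysis of the primary efficacy endpoint will be also repeated on the Complete case set (CCS) without missing data imputation as the sensitivity analysis". The Table 2.2 footnote defines sensitivity analysis 7 as the primary analysis without out-of-window values, and continues: "Sensitivity analysis 8 - Complete case set; Sensitivity analysis 9 - Complete case set excluding all FVC values outside of visit window". Neither document contains multiple imputation, a variance correction or a bootstrap. SAP 14 states: "The analyses methods in this SAP are fully consistent with the clinical study Protocol".

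**The concern.** The CIBASIC interval is the mean ± t(n−1) × s/√n over every record in the analysis data set. It is valid when each record is a separate observation. An SSD value is not one. Given the earlier visits, a mean of three independent donors has one third of the residual variance of a real Week 26 value. The donors are also already in the sample. So s is too small, n is counted in full, and no term reflects uncertainty about the imputed value.

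The trial has no control group and no hypothesis test on FVC. SAP 5 sizes it on precision and concludes that "60 patients included in the study will be sufficient for study parameters estimation". The 95% CI is therefore the main statement of what the trial has learned. Dropouts are not replaced, so imputed records make up part of the 60, and the stated precision improves as measured data are lost.

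**Working it through.** **1. The plan's own figures reproduce.** From SAP 5: 0.601 × 0.399 × (1.96/0.125)² = 58.96, taken as 60. Half-width at SD 20: 1.96 × 20/√60 = 5.06, the stated margin of about 5.

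**2. Inputs.** From the plan: % predicted FVC 67.8 (SD 11.24) at baseline and 65.3 (SD 14.52) at Week 26, so a true mean change of −2.5; n = 60; three donors; a two-sided 95% t-interval. Assumed: missing rates of 5, 10, 20 and 30%, missing completely at random; Week 12 mean 66.5 and SD 12.9; baseline–Week 26 correlation r of 0.87 to 0.93.

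SD of change = √(11.24² + 14.52² − 2r × 11.24 × 14.52) = √(337.2 − 326.4r):
- r = 0.87: 7.3
- r = 0.90: 6.6
- r = 0.93: 5.8

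The planning SD of 20 was also run.

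**3. Simulation, no deaths.** Trivariate normal FVC at Baseline, Week 12 and Week 26; SSD matching on the first two; t-interval on all 60 records; about 8,000 trials per cell (Monte Carlo error √(0.93 × 0.07/8000) ≈ 0.3 points). At r = 0.90:

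| Missing | SSD coverage | SSD width | Multiple imputation coverage | Width | Complete-case coverage | Width |
|---|---|---|---|---|---|---|
| 0% | 95.5% | 3.39 | 95.5% | 3.39 | 95.5% | 3.39 |
| 5% | 94.4% | 3.34 | 95.4% | 3.44 | 95.4% | 3.48 |
| 10% | 93.3% | 3.30 | 95.2% | 3.51 | 95.2% | 3.58 |
| 20% | 90.4% | 3.20 | 94.8% | 3.66 | 94.3% | 3.80 |
| 30% | 87.3% | 3.11 | 95.1% | 3.85 | 94.5% | 4.09 |

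The reported width falls to 3.30 and 3.20 at 10% and 20% missing, while 2 × 1.96 × the true standard error rises to 3.47 and 3.72.

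**4. Sensitivity to the assumptions (5/10/20/30% missing).**
- r from 0.87 to 0.93: coverage 94.1–94.4 / 93.2–93.3 / 90.4–91.0 / 87.3–88.5%.
- Planning SD of 20: 94.5 / 93.5 / 91.7 / 88.4%. At 20% missing the half-width is 9.75/2 = 4.9, against 11.19/2 = 5.6 with multiple imputation.
- Further runs with r from 0 to 0.9: 93.8–94.4 / 92.6–94.1 / 90.1–92.7 / 86.5–90.3%.
- If Week 12 FVC is missing too: 92.2–93.1% at 10% and 88.8–90.9% at 20%.

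**5. Deaths scored as 0 (r = 0.90).** With 2% deaths, SSD coverage is 90.1 / 88.6 / 87.5% at 0/10/20% other missing; multiple imputation gives 90.1 / 90.2 / 90.4%. With 5% deaths at 0/10/20/30%, SSD gives 91.2 / 90.2 / 90.6 / 90.1% and multiple imputation 91.2 / 90.6 / 91.6 / 91.6%. The width with 5% deaths is about 7.9, against 3.39 with none. Zeros dominate the width and cost coverage through skewness; the SSD part is at most about 3 points here.

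**6. Bootstrap repeating the SSD step** (no deaths, 200 resamples, 3,000 trials; 5/10/20/30% missing). Estimate ± t × bootstrap SE covers 94.5 / 94.6 / 95.7 / 95.1%, at 1.03 / 1.07 / 1.16 / 1.28 times the SSD width. The percentile interval covers only 93.4 / 93.1 / 93.9 / 94.0%.

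**The case against.** **Missing values may be few.** No rate is stated, and several provisions hold it down. Patients who stop treatment stay on schedule to Week 26, either of the two Week 26 measurements suffices, and out-of-window values stay in the primary analysis. The FAS needs a post-baseline efficacy assessment, first scheduled at Week 12, so very early losses generally drop out. The IPF Care Program aims to reduce dropout. At 5% missing the loss is under 1 point. This stands: rates of 20–30% have no support in the documents. But SAP 6.3 itself expects missed visits, withdrawals and transplants, and a pre-specified method should hold at plausible rates.

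**No deaths is unlikely.** The Protocol's GAP table gives stage I a 1-year mortality of 5.6%. At constant hazard that is 1 − √0.944 = 2.8% by 26 weeks, and the chance of no deaths among 60 is 0.944³⁰ = 18%. The life-expectancy exclusion and treatment could lower the rate; later stages would raise it. This also stands: with deaths present the SSD loss is smaller, and at 5% deaths it is slight.

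**No decision hangs on the interval, and complete-case results sit beside it.** At SD 6.6 and 20% missing, the half-widths of 1.60 (SSD) and 1.83 (multiple imputation) are both far inside the planned margin of about 5. Table 2.2 shows complete-case n and CI. This is partial mitigation. Those analyses exclude deaths, estimate a different quantity and do not correct the primary interval.

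**The Protocol prescribes SSD.** It prescribes the imputed value, but asks only for a 95% CI for the mean. The formula is the SAP's choice.

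**Conclusion.** The concern holds. The primary interval omits imputation variance for pattern-3 patients, as does the same interval in sensitivity analyses 1–7. That it is too narrow follows from the stated method; the size depends on assumptions. With n = 60, values missing completely at random and no deaths, nominal 95% coverage is about 94% at 5% missing, 93% at 10%, 90–92% at 20% and 87–88% at 30%. The missing rate, death rate, correlations and Week 12 moments are not in the documents. If dropout is informative, bias is a separate problem. This should be corrected, but it is not critical: the loss is small at low missing rates, and smaller again with 5% deaths scored as 0.

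**What to change.** Amend SAP 6.3, 7 and 8.1 so that the primary CI carries imputation uncertainty. SAP 2 allows revision before database soft lock.

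- **Option A (keeps the Protocol's point estimate).** Resample patients, repeat the SSD step in each resample, and report the estimate ± t × bootstrap SE, not the percentile interval. State that a donor drawn twice counts twice, and how such duplicates interact with Step 3's rule for tied distances. Cost: SAP wording and a bootstrap macro.
- **Option B.** Multiply impute pattern-3 Week 26 FVC from baseline and Week 12 FVC and combine by Rubin's rules. Keep SSD as a sensitivity analysis and record the departure from Protocol 6.2 in SAP 14.

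Use the same interval method for the SSD-based sensitivity analyses (1, 2 and 7), and label the LOCF intervals (3–6) as excluding imputation uncertainty.

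The price is a wider interval. With no deaths, Option A adds about 3% at 5% missing, 7% at 10%, 16% at 20% and 28% at 30%. With deaths the widening is smaller: about 2% and 5% at 10% and 20% missing with 2% deaths, and about 1% and 2% with 5% deaths. Neither option repairs the coverage lost to deaths scored as 0; in small checks with deaths, bootstrap coverage stayed at about 89–92%. A distribution-free CI for the median change already in Table 2.2 could be added as a supplementary summary of a different quantity.
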